1.3 Schedule of Activities

The treatment period will include 25 or 28 RT fractions, depending on local practice.

- The Schedule of Activities (SoA) is provided in [Table 1](#).
- The SoA for the Long-term Safety Follow-up is provided in [Table 2](#).
- **CCI** [REDACTED]
- The PK sampling schedule is provided in [Table 4](#).
- **CCI** [REDACTED]

Table 1 Schedules of Activities – 25 or 28 Fraction Days

		Evaluation Period											Notes
Study Period	Screening	Treatment Period/DLT Period (peposertib + capecitabine + RT)								Short-term Safety FU			Capecitabine given within 30 min after meal (AM and PM dosing), peposertib given 1 h after meal, RT given 1.5 h (\pm 30 min) after M3814 dosing. See Table 7 and Section 6.6.2.4.
Study Day	Day -28 to -1	FD1 to 25 or 28 Visits: on all FD (FD1 to FD25 or 28), FD25 or 28 is last RT day											
Peosertib Capecitabine RT		X: Peosertib qd 5 d/wk (only on FD) X: Capecitabine 825 mg/m ² bid 5 d/wk (only on FD) X: RT 1.8 Gy/fraction, 5 FD/wk, integrated concomitant boost (total daily dose 2 Gy) is allowed									Surgery		
Visit Week	-4 to -1	1	1	2	2	3	4	5	5 or 6	7 to 14	15	19	
Visit Day	-28 to -1	FD1	FD2	FD6	FD9	FD11	FD16	FD21	FD25 or FD28/ETT	In case of acute toxicities one visit/wk until recovery ^{a,b}	One visit / wk		If premature discontinuation during treatment, the SoA for FD25/FD28 should be performed. In such cases, this visit will be considered the ETT visit. ^a Where recovery means until the toxicity reduces to Grade 1 or to baseline Wk 14 visit is mandatory. ^b In case of a pandemic, it is per Investigator's discretion if these visits can be done via a phone call. Wk 14 visit remains a clinic visit.
Visit Window (Days)										\pm 7 for Wk 14 only/ \pm 2 for other visits	\pm 14	\pm 14	

Assessments and Procedures

Signed ICF	X												
Inclusion/Exclusion Criteria	X	X											
Demography	X												
Medical History	X												

		Evaluation Period											Notes
Study Period	Screening	Treatment Period/DLT Period (peposertib + capecitabine + RT)								Short-term Safety FU			Capecitabine given within 30 min after meal (AM and PM dosing), peposertib given 1 h after meal, RT given 1.5 h (± 30 min) after M3814 dosing. See Table 7 and Section 6.6.2.4.
Study Day	Day -28 to -1	FD1 to 25 or 28 Visits: on all FD (FD1 to FD25 or 28), FD25 or 28 is last RT day											

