4.1.3 Follow-up Periods

The study follow-up will include:

- **Short-term Safety Follow-up:** the duration of the Short-term Safety Follow-up is approximately 13.5 to 14 weeks after treatment completion, including 30 days after surgery, with an optional 1 visit per week from Week 7 to Week 14 in case of acute toxicities until recovery to Grade 1 or to baseline. For all participants, a mandatory visit will be performed at Week 14, approximately 1 to 2 weeks prior to surgery, including a tumor assessment with MRI (T_2 weighted and diffusion weighted) needed for restaging and evaluation. Additional details on tumor evaluation methods and response assessments are provided in Section 8.1.2.
- Surgical intervention must be performed 15 weeks (\pm 14 days) after start of study intervention/randomization (i.e. approximately 9.5 weeks after stopping RT), unless there are contraindications for surgery, or if the participant refuses. The last Short-term Safety Follow-up visit is scheduled for Week 19, approximately 4 to 6 weeks after surgical intervention/imaging/biopsy, as per SoC. During this visit, all safety information since the last visit, including surgical and/or biopsy morbidities/toxicities will be collected.
- **Long-term Safety Follow-up:** participants will be followed-up at 21 and 27 weeks after start of study intervention/randomization; every 3 months until 1 year after start of study intervention/randomization. Details on tumor evaluation methods and response assessments are provided in Section 8.1.2. Adjuvant chemotherapy is allowed as per local standards (see Section 6.5). Participants receiving adjuvant chemotherapy will continue to follow the schedule of activities (SoA) as per protocol. If adjuvant chemotherapy is given, any additional safety evaluations/laboratory tests will be as per local practice.
- Participants who have already been followed up for more than 1 year (Long-term Safety or Survival Follow-up) will be discontinued from the study after the approval of protocol amendment version 4.0 by the respective Health Authority and Ethics Boards. Participants will be informed of the discontinuation by the Investigator via a phone call. No further study visits or assessments are planned.

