- Procedures conducted as part of the participant's routine medical care (e.g. blood count) and obtained before signing of the ICF may be used for Screening or baseline purposes provided the procedures met the protocol-specified criteria and were performed within the time frame defined in the SoA (Section 1.3).
- Regarding the visits from Week 7 to 14 during the short-term safety follow-up ([Table 1](#)). The Week 14 visit is mandatory as this is needed for restaging and evaluation. All other visits in this period are optional and needed only in case of acute toxicities until recovery to Grade 1 or baseline.
- A maximum of 255 mL of blood will be collected in any one-month period from each participant in the study, including any extra assessments that may be required.

Screening:

Participants will be screened between Days -28 and -1, prior to first dosing on Day 1. Assessments and procedures to be performed at Screening are detailed in the SoA (Section 1.3). Screening-specific procedures include:

- **Demography:** date of birth, sex (gender), race, and ethnicity.
- **Medical history:** disease history, previous illness and surgeries (e.g. all during the past year and only major ones prior to that), concomitant illness, relevant medication, allergies, therapies stopped or changed at entry into the study, tobacco use including pack years, and alcohol use.
- **Eastern Cooperative Oncology Group Performance Status:** assessed at Screening to assess eligibility (Section 5.1) and then assessed according to the SoA (Section 1.3).
- **Chest-abdominal computerized tomography (CT):** A CT scan of the chest and abdomen will be performed prior to the beginning of study intervention to document the baseline status of the participant. Computerized tomography will be performed with intravenous iodinated contrast unless contraindicated. Evaluation up to 28 days prior to start of study intervention is allowed.

In the case of a rescreen and the screening CT scan is > 28 days from the previous screening scan, the screening CT will need to be repeated.

- **DRE and endoscopy (and EUS if indicated or if performed):** for participants who have received induction chemotherapy prior to start of study

Surgery

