Stop dates are not affected by this rule, e.g. a stop date of AEs, which starts prior to the cut-off, but stops after date of cut-off, will not be changed.

Significance level

All statistical tests mentioned in this IAP are to be regarded as exploratory. All statistical tests comparing study intervention groups will be performed two-sided. If confidence intervals are to be calculated, these will be two-sided with a confidence probability of 95%, unless otherwise specified in the corresponding section of this IAP.

Presentation of continuous and qualitative variables

Continuous variables will be summarized using descriptive statistics, i.e.

- number of participants, number of participants with non-missing values,

- mean, standard deviation,
- median, 25th Percentile - 75th Percentile (Q1-Q3),
- minimum, and maximum.

Qualitative variables will be summarized by counts and percentages.

Unless otherwise stated the calculation of proportions will be based on the number of participants in the analysis population of interest. Therefore, counts of missing observations will be included in the denominator and presented as a separate category.

For summaries by visits, only visits where all subsequent visits have 3 or more participants will be displayed. In case the analysis refers only to certain visits, percentages will be based on the number of participants in the corresponding analysis set.

Presentation of PK concentration data

Peposertib, its metabolite (if available), capecitabine, and its metabolite (if available) concentration data will be descriptively summarized using: number of non-missing observations (n), arithmetic mean (Mean), standard deviation (Sd), coefficient of variation (CV%), minimum (Min), median (Median), and maximum (Max). If $n \leq 2$, only n, Min, and Max will be reported.

Descriptive statistics of PK concentration data will be calculated using values with the same precision as the source data, and rounded for reporting purposes only. The following conventions will be applied when reporting descriptive statistics of PK concentration data:

Mean, Min, Median, Max: 3 significant digits

Sd: 4 significant digits

CV%: 1 decimal place

Presentation of PK parameter data

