15.4 Clinical Laboratory Evaluation

Population: SAF analysis set

Listings and summaries by visit will include all assessments, whereas shift tables and summaries of worst on-treatment values will not consider assessments after the on-treatment period.

Local laboratory values (including corresponding normal ranges) will be presented in summary statistics, shift tables and boxplots. In addition, liver toxicity will be assessed with Hy's Law analysis.

Laboratory results will be classified according to the NCI-CTCAE version 5.0. Additional laboratory results that are not part of NCI-CTCAE will be presented according to the categories: below normal limits, within normal limits and above normal limits (according to the laboratory normal ranges).

Common Terminology Criteria (CTC) gradable parameters

In this trial, Common Terminology Criteria (CTC) gradable parameters are the following:

Table 11 Common Terminology Criteria (CTC) gradable parameters

Category	Parameter (LBTEST)	Parameter code (LBTESTCD)	Name in NCI-CTC version 5.0	Direction of abnormality
Clinical Chemistry				
Electrolytes	Calcium	CA	Hypocalcemia/Hypercalcemia	Low/High
Electrolytes	Magnesium	MG	Hypomagnesemia/Hypermagnesemia	Low/High
Electrolytes	Potassium	K	Hypokalemia/Hyperkalemia	Low/High
Electrolytes	Sodium	SODIUM	Hyponatremia/Hypernatremia	Low/High
Enzymes/cardial	Creatine phosphokinase (CPK)	CK	CPK increased	High
Enzymes/liver	Alanine aminotransferase	ALT	Alanine aminotransferase increased	High
Enzymes/liver	Alkaline phosphatase	ALP	Alkaline phosphatase increased	High
Enzymes/liver	Aspartate aminotransferase	AST	Aspartate aminotransferase increased	High
Enzymes/liver	Total bilirubin	TBILI	Blood bilirubin increased	High
Metabolism	Glucose	GLUC	Hypoglycemia	Low
Metabolism	Uric acid ⁽¹⁾	URATE	Hyperuricemia	High
Plasma proteins	Albumin	ALB	Hypoalbuminemia	Low
Renal/kidney	Creatinine	CREAT	Creatinine increased	High
Renal/kidney	Creatinine clearance	CREATCLR	Chronic kidney disease	Low
Enzymes/cardial	Lactate dehydrogenase	LDH	Lactate dehydrogenase increased	High
Coagulation	Activated partial thromboplastin time	APTT	Activated partial thromboplastin time prolonged	High
Coagulation	International normalized ratio (INR)	INR	INR increased	High

Category	Parameter (LBTEST)	Parameter code (LBTESTCD)	Name in NCI-CTC version 5.0	Direction of abnormality
Hematology				
Platelets	Platelets count	PLAT	Platelet count decreased	Low
Red blood cells	Hemoglobin	HGB	Anemia/Hemoglobin increased	Low/High

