15.5 Vital Signs

Population: SAF Analysis Set

Body temperature, SBP, DBP, respiratory rate and heart rate will be analyzed with shift tables of maximum CFB of on-treatment assessments using the categories defined below:

Table 13 Vital signs categories

Parameter	Unit	Shift	Baseline categories	On-treatment categories (absolute change)
Temperature	°C	Increase	< 37 / ≥ 37 - < 38 / ≥ 38 - < 39 / ≥ 39 - < 40 / ≥ 40	< 1 ^a / ≥ 1 - < 2 / ≥ 2 - < 3 / ≥ 3
Heart rate	Bpm	Increase and decrease	< 100 / ≥ 100	≤ 20 ^a / > 20 - ≤ 40 / > 40
SBP	mmHg	Increase and decrease	< 140 / ≥ 140	≤ 20 ^a / > 20 - ≤ 40 / > 40
DBP	mmHg	Increase and decrease	< 90 / ≥ 90	≤ 20 ^a / > 20 - ≤ 40 / > 40
Respiratory rate	breaths/min	Increase and decrease	< 20 / ≥ 20	≤ 5 ^a / > 5 - ≤ 10 / > 10

a This category will include the subjects with no changes or decrease/increase in the increase/decrease part of the table, respectively.

Line plots per dose level and overall will be produced for systolic blood pressure, diastolic blood pressure, heart rate, temperature and weight. These will be presented by visit.

Maximum change from baseline will also be listed for each parameter and participant and will include: Dose level, subject ID, parameter, visit, date, unit, baseline value and maximum change from Baseline for each participant. This listing will be sorted by dose level, subject ID, parameter and visit.

Finally, all vital signs data from “Vital Signs” eCRF pages will be listed.

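### By-visit lab and vital-sign displays for Weeks 7-13 describe only participants with an unresolved acute toxicity, and the SAP does not set these visits apart

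*Protocol*

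**What the plan says.** **When participants are seen.** For Weeks 7 to 14, Table 1 of the protocol (Section 1.3) reads "In case of acute toxicities one visit/wk until recovery", with recovery meaning Grade 1 or baseline. Section 8 repeats the condition: "All other visits in this period are optional and needed only in case of acute toxicities until recovery to Grade 1 or baseline". Week 14 is different: "The Week 14 visit is mandatory as this is needed for restaging and evaluation". After that everyone is due again: "The last Short-term Safety Follow-up visit is scheduled for Week 19", and Table 2 schedules Weeks 21, 27, 39 and 52.

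**What is measured.** In the Week 7 to 14 column, vital signs, physical examination (with weight), hematology and serum chemistry carry a plain mark. Coagulation and urinalysis in the same column are restricted to Week 14. Labs and vital signs are therefore meant to be taken at the conditional visits. A footnote adds: "In case of a pandemic, it is per Investigator's discretion if these visits can be done via a phone call".

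**How it is displayed.** SAP 15.4 states: "Listings and summaries by visit will include all assessments". It also plans boxplots of hematology and biochemistry values by time point. SAP 15.5 states: "Line plots per dose level and overall will be produced for systolic blood pressure, diastolic blood pressure, heart rate, temperature and weight", presented by visit. The plotted statistic is not named. SAP 15.6.2 confines ECG summary tables to scheduled visits; 15.4 and 15.5 have no such sentence. For by-visit summaries in general, SAP Section 9 sets one rule: "only visits where all subsequent visits have 3 or more participants will be displayed".

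**The concern.** A by-visit table or line plot is normally read as one group followed over time. Here the group changes. It is all treated participants up to FD25/28, then only those whose acute toxicity has not recovered, then all participants again at Week 14. People leave the Weeks 7-13 set because they recover, so membership depends on outcome. A movement in the curve at these weeks may reflect who attended rather than any change within participants.

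Safety and tolerability is a secondary objective, and the SAP presents results by dose level and overall. A reader of the study report could take a shift after treatment, or a return at Week 14, as a feature of the regimen.

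**Working it through.** The plan states no figure on this point, so there is none to reproduce. The check cross-reads the schedule against the SAP and adds illustrative arithmetic.

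**1. Which weeks are affected.** The treatment period ends at Week 5 to 5.5 (protocol Section 4.1). The SAP on-treatment period runs to last administration + 30 days:
- 5 + 30/7 = 9.3 weeks
- 5.5 + 30/7 = 9.8 weeks

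For a participant who completes treatment, Weeks 7-9 are still on-treatment and about Weeks 10-13 are not. Only Weeks 7-13 are toxicity-triggered. If each optional week is tabulated separately, the post-baseline lab time points are 5 on treatment (FD6, 11, 16, 21, 25/28) + 7 optional + 6 later (Weeks 14, 19, 21, 27, 39, 52) = 18, of which 7 are conditional. Table 1 has a single column for Weeks 7 to 14, so separate tabulation is an assumption.

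**2. Size of the shift.** Let N be all participants, k those attending, and d the mean difference between attendees and the rest, in SD units. Then attendee mean − full-set mean = d × (N − k)/N. N = 19 is the number treated as of 06 May 2021 (protocol Synopsis). The values of k and d are assumed, because the documents give neither.

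| d (SD) | k = 5: × 14/19 | k = 3: × 16/19 |
|---|---|---|
| 0 | 0 | 0 |
| 0.5 | 0.37 | 0.42 |
| 1 | 0.74 | 0.84 |

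Fewer attendees give a larger shift for the same d.

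**3. Where the subset would be visible.** Suppose a limit of 3 applied at the visit itself. With each participant attending independently with probability p (assumed), the chance that at least 3 attend is:

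| n | p = 0.1 | p = 0.3 | p = 0.5 |
|---|---|---|---|
| 19 (overall) | 0.30 | 0.95 | 1.00 |
| 6 | 0.02 | 0.26 | 0.66 |
| 3 (planned cohort) | 0.001 | 0.03 | 0.13 |

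With n = 3 the week appears only if all 3 attend, and then there is no selection. The overall display and larger dose levels carry the problem.

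**4. The Section 9 rule as written.** It looks at the counts of later visits, not of the visit shown. Assume overall counts of 19 through FD25/28; 6, 5, 4, 4, 3, 3, 2 at Weeks 7-13; 18 at Week 14; and 15 to 17 afterwards.
- Literal reading: the count of 2 at Week 13 suppresses every visit before it, including baseline and all treatment visits. Week 13 itself is shown with n = 2.
- With 8, 7, 6, 5, 4, 3, 3 instead, all visits appear, including all seven selected weeks.
- Reading it as a limit of 3 at the visit itself, the first set of counts still shows selected Weeks 7-12.

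No reading removes the selection from the overall display.

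**The case against.** The trigger is any acute toxicity, not an abnormal lab value or vital sign. Protocol Section 2.3 names radiation dermatitis and mucositis as acute radiotherapy effects. Someone attending for persistent dermatitis need not have an unusual sodium or blood pressure. This stands: for many parameters d may be near zero, which is why the range in the working starts at 0.

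Little is decided on these displays. No formal tests are planned, the primary endpoint is DLT within the treatment period, and the lab endpoint is Grade 3 or higher abnormality. That endpoint is served by worst-grade shift tables and a dedicated listing. This also stands and limits the weight of the point. By-visit tables print the number of non-missing values, so a fall in attendance would show. A count does not, however, tell the reader that those remaining were selected for unresolved toxicity.

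Three stronger readings are tempting, and the documents do not support them:
- A reader might infer that post-treatment summaries in general are distorted. Week 14 and Weeks 19 to 52 are for all participants, and about Weeks 7-9 are on-treatment by SAP definition. The rule taking in all assessments is stated for labs only; for vital signs the issue is the line plots.
- A reader might infer a certain apparent deterioration that cannot show recovery. A lab value can normalise while the triggering toxicity persists, and a toxicity can improve from Grade 3 to 2 while visits continue.
- A reader might infer a broad distortion of dose-level comparisons. With a planned cohort of 3, a display limit of 3 at the visit would rarely show an optional week, and never a partial one.

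The number of optional visits with lab data is also unknown, since some may have been phone calls.

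**Conclusion.** The point holds within these limits. Applied as written, SAP 15.4 and 15.5 place a toxicity-selected subset between the all-participant FD25/28 and Week 14 visits, without marking it. It matters mainly in the overall display and in dose levels with more than 3 participants. The illustrative error is 0 to about 0.84 SD, for an assumed difference of 0 to 1 SD with 3 to 5 of 19 attending. Its direction cannot be stated in advance. The literal Section 9 rule adds a separate defect: a sparse optional week can remove earlier visits that everyone attended. The primary DLT analysis and the Grade 3 or higher lab listing are unaffected. This is a worthwhile correction to descriptive safety displays and does not threaten the trial's conclusions.

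**What to change.** In SAP 15.4 and 15.5, limit by-visit tables, boxplots and line plots to visits scheduled for all participants: baseline, the treatment visits, Week 14, and Week 19 onward. Apply the Section 9 count rule to those visits only. Optional weeks then cannot trigger suppression, although the rule's wording would still let a late visit thinned by dropout do so.

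Keep Weeks 7-13 values, flagged, in the listings. Keep them in the shift and worst-value analyses exactly as the SAP already defines these, that is, on-treatment to last administration + 30 days. Report by dose level how many participants had at least one optional visit.

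The cost is SAP wording only. The downside is that by-visit displays show no point between FD25/28 and Week 14. Lab and vital-sign values after the on-treatment period (about Weeks 10-13) would appear in listings only, because the shift and worst-value tables already exclude them.
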